## **PROVISIONS TO MONITOR THE DATA TO ENSURE THE SAFETY OF PARTICIPANTS**

The purpose of this study is to develop a novel treatment to help reduce pain through dynamic AI-guided visual stimuli. The Data and Safety Monitoring Plan (DSMP) outlined below for this Phase I grant proposal will adhere to the protocol approved by the IRB, as well as by all other committees that have oversight responsibilities for this research. Since the study entails only minimum risk to the participants, the PI will monitor the safety of the participants. The Study team members will compile data and report to PI, as well as to the funder.

Our biosensor recordings have the potential to pick up abnormalities, including signs of focal and general epileptiform and non-epileptiform waveforms (EEG); arrhythmias, ischemia, and conduction abnormalities (ECG); and radicular abnormalities and metabolic-related conduction disorders (EMG).

### ***Adverse Events associated with Experiment 1***

Regarding the visual stimuli, adverse events are:

- seizure, defined as jerking movements of the limbs and/or loss of consciousness,
- dizziness/vertigo as defined by verbal complaints and loss of balance, and syncope.

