## Description of the procedures used in the study

**Nociceptive protocols:** Participants will be attached to the biosensors and seated in front of a digital display. Pain induction will be carried out as follows.

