### ***Adverse Events associated with Experiments 2***

We are concerned that pain induction and visual stimulation each has the potential for creating adverse effects, although they are unlikely to occur. CHEPs stimulation is commonly used pain-induction models for experimental purposes. It has been well described and are known to have a very low potential for harm to study volunteers because the stimuli can be precisely controlled. Within the individually predetermined range of nociceptive stimulation, participants are expected to experience neither psychological distress nor tissue injury. The latter will be verified by study personnel through inspection of the involved skin after the first test stimuli are administered (during the initial demonstration of study procedures to participants) as well as after all nociceptive stimulation has concluded. Furthermore, the study team members involved in pain induction will be present throughout and observe the participants directly during the entire process. In the highly unlikely event of equipment malfunction or misapplication, both of which

would trigger the need for reporting, arrangements will be made for participants to be evaluated by the on-site physician as stipulated in the protocol.

With regard to pain stimuli, adverse events are:

- excessive intensity of induced pain, defined as 80-100mm on VAS,
- anxiety/fear, defined as a 100% increase (i.e., doubling) in heart rate or >135 beats per minute, and
- injury to skin, likely in the form of a burn, defined as skin discoloration (i.e., red, white and/or brown) that does not resolve within 10 minutes of stimulus discontinuation.

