## **WITHDRAWAL OF PARTICIPANTS**

There are minimal risks to be incurred from participating in this study. Specific risks related to the clinical and cognitive assessments (study questionnaires), visual stimulation are described below.

Participants will be reminded that they may stop participating in the study at any time for any reason with no penalty or loss of benefits to which they are otherwise entitled. Participants will be encouraged to take breaks when needed. They will be reminded that they may refuse to answer any questions on the study questionnaires, and they may stop the nociceptive stimulation session at any time.

During arousal experiments, since the risk of adverse medical effect is extremely low and participants inclusion criterion bars participants with sensitivity to visual stimulation, any adverse effects will be dealt with through usual emergency procedures (calling 911).

Syncpe, vasovagal response, signs of seizure, and verbal complaints of dizziness and vertigo will be considered as criteria for terminating the experiment. The Project Coordinator on site will be responsible for reporting all events to the PI and Safety Officer within a day, and these events will then be reported to the NIH and IRB according to the following scheme:

- Unanticipated problems, complaints and serious adverse events will be reported to NIH and IRB within 5 days
- Unanticipated Adverse Device Events and Major deviations within 10 days.
- Minor deviations will be aggregated and reported with continuing review or study closure.

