## **SHARING OF RESULTS WITH PARTICIPANTS**

There is a potential for observing abnormalities in our biosensor recordings. For example, with EEG recordings, we can observe signs of focal and general epileptiform and non-epileptiform waveforms; with ECG, we can observe arrhythmias, ischemia, and conduction abnormalities; and with EMG, we can observe radicular abnormalities and/or metabolic-related conduction disorders. Given that records are not performed for diagnostic purposes, if abnormalities are suspected the participant will be informed that such an abnormality was observed and instructed to follow up with their health provider for further investigations.

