## **CONFIDENTIALITY**

Participation in this research will be kept confidential. In compliance with HIPAA protocols, all presentations of data will be void of unique identifiers in order to ensure that participant confidentiality is maintained. The experiment preparation will be conducted in a dedicated room with only the participants, the experimenter and the assistants present. In the beginning of the experimental setup a participant will be requested to sign a consent form, in which the experimental procedures and their rights as participants will be explained. The participants will be asked to provide general demographic information consisting of their age, gender and race/ethnicity. During the setup the electrodes will be attached to the participant's head, face, hands and palms, so participants will not be required to disrobe. The experiment will be conducted in a separate experimental booth, in which the participant will either be alone or with the experimenter depending on the specific details of the experiment.

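### Read literally, dizziness from the video is an adverse event only with loss of balance, although a verbal complaint alone is enough to end the experiment

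*Combined protocol and SAP*

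**What the plan says.** The plan has one list of adverse events from the visual stimuli, in *Adverse Events associated with Experiment 1*. It has two items. The first is "seizure, defined as jerking movements of the limbs and/or loss of consciousness". The second is "dizziness/vertigo as defined by verbal complaints and loss of balance, and syncope".

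The criteria for ending a session are in *Withdrawal of Participants*. Besides syncope, a vasovagal response and signs of seizure, "verbal complaints of dizziness and vertigo will be considered as criteria for terminating the experiment". No balance sign is attached to that criterion. The same section has the on-site coordinator report all events to the principal investigator and the Safety Officer within one day. It also lists complaints among the matters that go to NIH and the IRB within 5 days.

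On posture, *Description of the procedures used in the study* says: "Participants will be attached to the biosensors and seated in front of a digital display". That sentence stands under the nociceptive protocols. The Experiment 1 section states no posture.

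**The concern.** The video is the intervention under study, and the adverse-event list is where its harms are defined. If the event definition asks for more than the stopping rule does, a session can be ended because of the video without producing any listed adverse event of the video. Staff who apply both sections as written would stop and report the participant, and could then correctly leave that participant out when compiling adverse events. The plan's stated long-term aim is a treatment that is safe as well as effective, so ascertainment of the most ordinary complaint about a moving visual stimulus should not depend on a conjunction.

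**Working it through.** No power, alpha or rate enters this point, and the plan gives no figure to reproduce. The check compares the texts.

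**Step 1: what the conjunction means.** The dizziness item joins its two signs with *and*; the seizure item immediately above joins its two with *and/or*. Where the authors meant that either sign suffices, they had the wording for it and used it one line earlier. The plain reading of the dizziness item is therefore that both signs are needed. The trailing mention of syncope is best read as a separate event, since the withdrawal section also lists syncope on its own.

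**Step 2: apply both sections to each possible presentation.**

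| Presentation | Stop on the dizziness criterion? | Adverse event, literal reading? | Adverse event with *and/or*? |
|---|---|---|---|
| Complaint only | Yes | No | Yes |
| Complaint and loss of balance | Yes | Yes | Yes |
| Loss of balance only | No | No | Yes |

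The first row is the problem: a stop that is not a listed event. With *and/or*, every dizziness stop is also an event.

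**Step 3: express the shortfall.** Let S be the number of participants stopped for a dizziness complaint and B the number of those who also lose balance. Among those stopped, the literal definition counts B, so the shortfall is S − B. It lies between 0 (all lose balance) and S (none do). The documents give neither S nor B.

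For scale only, assume that 1% to 10% of Experiment 1 at its cap of 100 complain of dizziness without losing balance. Then S − B would be 0.01 × 100 = 1 to 0.10 × 100 = 10 participants. That range is an assumption with no support in the documents and is not an estimate.

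**Step 4: does posture settle B?** Experiment 1 uses a display and the same four recording types as Experiment 2, so participants are probably seated there too. A seated person is less likely to show loss of balance during a clip, which would make B smaller than S. But it could still appear in the 45-second breaks or on standing up afterwards. The criterion would be insensitive, not impossible to meet, and posture gives no number.

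**The case against.** The best reply is that *and* may simply list the ways in which dizziness shows itself. The stopping sentence also uses *and* to join alternatives, and nobody would require all of those before stopping. This reading is possible. The neighbouring *and/or* makes it less likely, and if it was intended, the same edit is needed to make it clear.

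Second, a stopping threshold below an event definition is protective and not a contradiction in logic. That is right, and the stopping rule should stay as it is. What remains is that a complaint serious enough to end a session need not count as an event of the stimulus.

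Third, the withdrawal section's reporting routes catch the case anyway. This stands and limits the effect: the stop is reported. Reporting it does not, however, make it meet the adverse-event definition.

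A reader might also infer something stronger: that seizure or syncope in Experiment 1 could go unseen. In Experiment 2 "the study team members involved in pain induction will be present throughout and observe the participants directly during the entire process", whereas the *Confidentiality* section describes a booth "in which the participant will either be alone or with the experimenter depending on the specific details of the experiment". The documents do not support that inference. The booth sentence concerns who is in the room, and being alone there is not the same as being unobserved. The Experiment 1 optimization method has the team monitoring responses during stimulus presentation, and the trial structure asks for a behavioural response after each clip. The laboratory figures, and pages that follow the laboratory description, are also missing from the text available for review; a window or live view could be described there. Observation in Experiment 1 is at most a detail left unstated.

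**Conclusion.** The point holds as an inconsistency of wording. On the literal reading, the adverse-event definition for dizziness/vertigo is narrower than the stopping criterion for the same complaint. A participant stopped for a complaint alone could be left out of the adverse events attributed to the video.

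This rests on two assumptions: that *and* means both signs, which the seizure item supports but does not prove, and that adverse events of the video are compiled from this list.

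The size cannot be derived from the documents. A reader might infer that the adverse-event count for dizziness would read zero while sessions were being ended for it. That goes too far: the plan describes no adverse-event rate or table, gives no dizziness frequency, and does not state that Experiment 1 participants are seated. The change is still worth making, because it is specific, nearly free, and improves ascertainment of harm from the intervention itself.

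**What to change.** In *Adverse Events associated with Experiment 1*, define dizziness/vertigo as a verbal complaint and/or loss of balance, and keep syncope as a separate event. Leave the stopping criterion in *Withdrawal of Participants* unchanged. Record for each case whether balance was lost, so that complaint-only cases can be told apart from those with an outward sign.

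The cost is a change of conjunction and one recorded item. The downside is that the count will rise and will include mild complaints; the balance item lets a reader separate these. Sample size, endpoints and session length are unaffected.

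Optionally, the sponsor could state that participants stay in sight during Experiment 1 clips, through a window or by live view. This would clarify the text but does not correct a demonstrated error. Either arrangement avoids placing a person in the booth who might affect the arousal measures.

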### ***Adverse Events associated with Experiments 2***

We are concerned that pain induction and visual stimulation each has the potential for creating adverse effects, although they are unlikely to occur. CHEPs stimulation is commonly used pain-induction models for experimental purposes. It has been well described and are known to have a very low potential for harm to study volunteers because the stimuli can be precisely controlled. Within the individually predetermined range of nociceptive stimulation, participants are expected to experience neither psychological distress nor tissue injury. The latter will be verified by study personnel through inspection of the involved skin after the first test stimuli are administered (during the initial demonstration of study procedures to participants) as well as after all nociceptive stimulation has concluded. Furthermore, the study team members involved in pain induction will be present throughout and observe the participants directly during the entire process. In the highly unlikely event of equipment malfunction or misapplication, both of which

would trigger the need for reporting, arrangements will be made for participants to be evaluated by the on-site physician as stipulated in the protocol.

With regard to pain stimuli, adverse events are:

- excessive intensity of induced pain, defined as 80-100mm on VAS,
- anxiety/fear, defined as a 100% increase (i.e., doubling) in heart rate or >135 beats per minute, and
- injury to skin, likely in the form of a burn, defined as skin discoloration (i.e., red, white and/or brown) that does not resolve within 10 minutes of stimulus discontinuation.

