## **Experiment 2. Optimization of visual stimulation for pain perception**

In this experiment we will optimize visual stimulation with the goal of reducing pain perception. To reduce the burden on participants, optimization has been designed as a two-step process, with the first step (implemented in Experiment 1) requiring no pain induction. Our preliminary hypothesis is that arousal-inducing visual stimuli will reduce the perception of acute pain, based on the well-known phenomenon of stress-induced analgesia (Vachon-Presseau et al., 2013; Yilmaz et al., 2010). Thus, once we optimize the stimuli to affect arousal state in Experiment 1, we will test the effectiveness of the optimized visual stimuli (OVS) in reducing pain perception and carry out additional adjustments to further increase their impact.

Location	Dandelions Science Laboratory 
Estimated number of participants	20 participants
Estimated experiment duration	2 hr

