### ***Goals***

1. Find optimized visual stimuli
2. Determine optimization curve
3. Disentangle anxiety and pain responses

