### ***Equipment and instruments***

1. Neurophysiological assessment: EEG, GSR, EMG, ECG
2. Behavioral assessment: VAS

3. Visual stimulation: DVN presented on a display
4. Infrastructure: 2 laptops / PCs for rendering & processing of the data
5. Nociception: Contact Heat Evoked Potentials (CHEPs)

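### The Experiment 2 adverse event anxiety/fear is defined by heart rate alone, so reported fear below the threshold is not recorded under it, while a qualifying rise from pain or induced arousal is

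*Combined protocol and SAP*

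**What the plan says.** All references are to the combined protocol and SAP.

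- **The definition.** The section on adverse events for Experiment 2 lists three events tied to pain stimuli. The second reads "anxiety/fear, defined as a 100% increase (i.e., doubling) in heart rate or >135 beats per minute, and"; the closing word only joins it to the third item, skin injury. The definition has no self-report, no observer judgement and no attribution step. It does not say which heart rate the doubling is measured from.
- **The expectation and its check.** The same section says that "participants are expected to experience neither psychological distress nor tissue injury", and then "The latter will be verified by study personnel through inspection of the involved skin". The check covers tissue injury only; none is described for distress.
- **Other subjective events.** Excessive pain is defined in the same list by a VAS range. The Experiment 1 list has "dizziness/vertigo as defined by verbal complaints and loss of balance, and syncope", so verbal complaint is already part of a definition elsewhere.
- **Measures in the session.** Under equipment and instruments for Experiment 2 the only behavioural measure is "Behavioral assessment: VAS". The self-assessment manikin is listed for Experiment 1, and the Perceived Stress Scale is completed before the experimental blocks begin.
- **The intervention.** The working hypothesis of Experiment 2 is that "arousal-inducing visual stimuli will reduce the perception of acute pain".
- **General reporting.** The section on withdrawal of participants states: "Unanticipated problems, complaints and serious adverse events will be reported to NIH and IRB within 5 days". It also lets participants stop at any time.

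**The concern.** Fear is something a person reports or shows. Here it is replaced by an extreme value of one physiological signal, and that can go wrong in two directions. A frightened participant whose heart rate rises moderately does not meet the definition. A participant who is not frightened but whose heart rate crosses the line does meet it, and in this experiment heart rate has at least two other reasons to rise: the painful stimulus and stimuli chosen to induce arousal.

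What is at stake is the meaning of the safety record. This is the only listed event that names a psychological state, and no in-session anxiety rating is listed that could recover what it misses. A record showing no anxiety/fear events would say little about whether participants were afraid, and a record showing some would not establish that fear was the cause.

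**Working it through.** The plan gives no figure to reproduce here. The check is how large a rise the definition demands, followed by a comparison of the relevant sections.

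**Inputs.** From the protocol: a doubling of heart rate, or a rate above 135 bpm, whichever is met first. Not in the protocol: the reference rate H, which is therefore an assumption shown over a range.

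**Formula.** Doubling needs a rise of H. Passing 135 bpm needs a rise of just over 135 − H. The smallest qualifying rise is therefore min(H, 135 − H). The two are equal when H = 135 − H, that is, at H = 67.5 bpm. Below that rate doubling is met first; above it the 135 bpm limit is.

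| Assumed H (bpm) | Rise to double | Rise to 135 | Smallest qualifying rise |
|---|---|---|---|
| 50 | 50 | 85 | 50 |
| 60 | 60 | 75 | 60 |
| 67.5 | 67.5 | 67.5 | 67.5 (the maximum) |
| 70 | 70 | 65 | just over 65 |
| 75 | 75 | 60 | just over 60 |
| 80 | 80 | 55 | just over 55 |
| 90 | 90 | 45 | just over 45 |
| 100 | 100 | 35 | just over 35 |

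For H of 60 to 80 the required rise lies between about 55 and 67.5 bpm. It is smaller when the reference rate is already high, so the undefined reference matters: a rate taken when the participant is already tense gives a different rule from one taken at rest.

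**Missed event, applied literally.** H = 70, the participant says they are afraid and ends the session, peak 105 bpm. The rise is 105 − 70 = 35, or 35/70 = 50%. This is neither a doubling nor above 135, so no anxiety/fear event is recorded.

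**Mislabelled event, applied literally.** H = 75, no fear reported, peak 136 bpm during pain stimulation. The rate exceeds 135, so an anxiety/fear event is recorded.

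**Sections side by side.** The Experiment 1 list uses verbal complaint for dizziness, and the Experiment 2 list uses a self-rated scale for pain. Anxiety/fear is the one subjective state in these lists with no subjective element in its definition. The text that expects no distress and no tissue injury then provides a check on the second only.

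**The case against.** The strongest reply is that fear is not lost to oversight. Complaints go to NIH and the IRB within 5 days, in the same tier as serious adverse events. The site coordinator reports all events to the PI and Safety Officer within a day. Staff watch participants throughout pain induction, and participants may stop whenever they wish. This stands, and it limits the point: a voiced complaint has a written route, though not under this heading. Someone who stops without complaining is less clearly covered.

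Second, the list concerns pain stimuli in seated volunteers without cardiac disorders, so a qualifying rise cannot be said to be labelled fear whatever its cause. That also stands. What remains is that nothing in the definition separates fear from pain or from stimulus-driven arousal. The documents give no basis for saying how often this would happen.

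Third, an objective cut-off is reproducible, whereas spontaneous report has no severity floor, so ordinary apprehension before a heat stimulus could be recorded. This is a real cost, but it does not make heart rate a measure of fear, and the cut-off can be kept under its own name.

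A reader might also infer that the trial cannot support its own safety statement. The documents do not carry that: the sentence on distress is an expectation within a risk description, the endpoints are VAS and ERP, and no adverse-event analysis is planned. Nor is the Experiment 2 goal "Disentangle anxiety and pain responses" at issue. It is a research goal that does not depend on this definition and that the change would not advance.

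**Conclusion.** The concern holds as misclassification and under-capture under one adverse-event heading. Reported fear is outside the definition unless heart rate rises by about 55 to 67.5 bpm (assumed H of 60 to 80) or just over 35 bpm (assumed H of 100). A qualifying rise from pain or induced arousal falls inside it. The two-way error follows from the text alone; only the size of the rise rests on an assumed reference rate.

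It is tempting to go further and predict how many of the 20 participants would be missed. The documents give neither a resting rate nor the rise that fear produces, and the answer depends heavily on both. Suppose all 20 were frightened, with a mean rise of 40 bpm and resting rates normally distributed with SD 10 bpm and mean 65 to 75. If everyone has exactly the same rise, about 0.15 to 0.5 of 20 would be flagged. If the rise varies between people with an SD of 10 to 20 bpm, it is about 1 to 4 of 20. Most would be missed in each of these cases, but no single count can be defended, and the conclusion does not need one.

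**What to change.** In the adverse-event section for Experiment 2, replace the single line with two events:

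1. **Anxiety/fear:** recorded when the participant reports it, or stops the session because of it, whatever the heart rate.
2. **Heart-rate event:** recorded under its own name, using the thresholds already written, unchanged.

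This alters what is recorded and what it is called. It does not alter any threshold, the stimulation, or the criteria for ending a session. The cost is two lines of text. Staff already observe participants during pain induction, so no procedure is added. The downside is that more mild events will be recorded.

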### ***INCLUSION CRITERIA***

- Participants of both sexes
- Participants of diverse ethnic and racial backgrounds
- Subjects who speak, read, and understand English and are willing and able to provide written informed consent on an IRB-approved form prior to the initiation of any study procedures
- Age range: 18-50

The age limitation reflects differences in pain response thresholds both in terms of mean and variance, across different developmental groups (González-Roldán et al., 2020; Tumi et al., 2017). Moreover, the age range stated above is the target group of individuals of greatest interest for this future intervention (Salmond & Allread, 2019).

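### The adverse event definition of skin injury covers only persistent red, white or brown discoloration, which is narrower than the tissue injury that the planned skin inspections are meant to rule out

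*Combined protocol and SAP*

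**What the plan says.** The section Adverse Events associated with Experiments 2 introduces its list with "With regard to pain stimuli, adverse events are". Three items follow: excessive pain, anxiety or fear, and skin injury. There is no catch-all item. The skin item reads "injury to skin, likely in the form of a burn, defined as skin discoloration (i.e., red, white and/or brown) that does not resolve" and ends with the time limit "within 10 minutes of stimulus discontinuation".

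Earlier in that section, participants are expected to have no tissue injury, and this is to be "verified by study personnel through inspection of the involved skin after the first test stimuli are administered" and again once all nociceptive stimulation is over. The signs that staff should look for are not listed.

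The Inclusion Criteria ask for "Participants of diverse ethnic and racial backgrounds". The Withdrawal of Participants section adds a general reporting rule: "Unanticipated problems, complaints and serious adverse events will be reported to NIH and IRB within 5 days".

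**The concern.** Skin damage is the one tissue harm that the protocol names for the pain stimuli, and it names a burn as the likely form. A safety summary for Experiment 2 will probably tabulate skin adverse events by this definition. If the definition admits color alone, and only three colors, an injury that shows itself in another way drops out of that count even when staff have seen it.

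Two things are at stake. First, a statement that no skin adverse events occurred would not mean that no tissue injury occurred, although a reader would take it so. Second, if the listed colors are harder to see on some skin tones, the undercount could be uneven across the participants whom the trial sets out to include.

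**Working it through.** No arithmetic applies to the definition, and the plan gives no figure to reproduce. The check is a reading of the wording, followed by a search for anything elsewhere that widens it.

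**Step 1: is color the whole criterion?** The item says what skin injury is *defined as*, and introduces the colors with *i.e.*, not *e.g.* Read literally, discoloration is the full definition and red, white and brown are the full set of colors. The list around it is closed.

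**Step 2: does another section widen it?** The sections on safety monitoring, adverse events in Experiments 1 and 2, withdrawal, and risks contain no general definition of an adverse event and no second skin criterion. Blister, swelling and broken skin are not named in any of them.

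**Step 3: apply the definition to possible findings at the thermode site.**

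| Finding | Skin adverse event as written? |
|---|---|
| Red, white or brown change still present after 10 minutes | Yes |
| The same change, gone by 10 minutes | No |
| Blister or swelling with one of these colors, persisting | Yes, through the color |
| Blister, swelling or broken skin without a listed color | No |
| Color change not visible as one of the three | No |

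The second row is the protocol's own persistence rule and is not in dispute. The last two rows are the gap.

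**Step 4: compare with the purpose of the inspection.** The inspections are there to verify that there is no tissue injury. The findings in the fourth row are tissue injury in ordinary usage. The inspection could therefore find something that contradicts the safety expectation and yet meets no adverse event definition in the same section.

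**Step 5: what one event would mean.** Experiment 2 states 20 participants, so one uncounted injury moves the observed proportion by 1/20 = 5 percentage points. With the 30 participants in the sample size paragraph it would be 1/30 = 3.3 points. This shows how much one event weighs in so small a sample; it does not estimate how often one would be missed.

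**The case against.** The strongest reply is that little would escape notice. Staff are present throughout, the two inspections are not restricted to color, and a blister would be seen. The Withdrawal of Participants section sends complaints, unanticipated problems and serious events to the NIH and IRB within 5 days and unanticipated device events within 10 days, and none of these routes depends on the color list. The adverse event section also has a reporting route that begins "In the highly unlikely event of equipment malfunction or misapplication, both of which". All of this stands. A reader might infer that injuries without a listed color would go unseen or unreported, and the documents do not support that.

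These routes do not close the gap in counting. The protocol itself names a burn, so it is doubtful that one is unanticipated. A complaint depends on the participant, and an injury can occur without malfunction or misapplication. None of the routes makes the finding a skin adverse event.

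Three other stronger readings should be set aside:

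- A reader might infer that the colors are absolute, so that existing marks would be counted. Discoloration that fails to resolve after the stimulus already implies a change from the participant's own skin. The surrounding forearm also offers some comparison, since the thermode is only 27 mm across. A look beforehand is a refinement.
- A reader might infer that a blister or swelling never counts. It does count when a listed color accompanies it and persists. The documents do not say how often that would be.
- A reader might want a percentage of injuries missed. The documents give neither an injury rate, nor the mix of skin tones, nor the sensitivity of a color check, so any such figure would be invented.

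**Conclusion.** The concern holds in a limited form. The definition of skin injury is too narrow for the purpose stated in its own section, because an injury without a visible red, white or brown change lasting more than 10 minutes is not counted as a skin adverse event. This follows from the wording alone for blister, swelling and broken skin.

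The part about skin tone rests on an added assumption, that a color change can be harder to recognize as one of the three on some skin. The documents do not say so. It is plausible given the inclusion of diverse racial backgrounds, and the main conclusion does not need it.

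The size cannot be quantified. No efficacy endpoint or analysis is affected, and inspection and general reporting remain as a backstop. This is a correction that should be made, not one on which the trial's validity depends.

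**What to change.** In Adverse Events associated with Experiments 2, reword the skin item so that it covers any visible change at the stimulated site compared with its appearance before the first stimulus: color change of any kind, blister, swelling or broken skin. Keep the existing 10-minute persistence condition for color change. State whether it also applies to swelling; otherwise any brief swelling would count with no time limit.

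Name the same signs for the two inspections already planned, so that what staff look for matches what is counted. Add a brief look at the site when the thermode is attached, to serve as the reference.

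The cost is one reworded sentence, a line on the inspection signs and a few seconds per participant, with no new staff or equipment. The downside is that a few more minor events may be recorded. Only what is recorded changes; the stimulation and its management are untouched.
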